**Table 1 Protocol-Required Safety Laboratory Assessments**

Laboratory Assessments	Parameters
Hematology	

Leucocytes, erythrocytes, hemoglobin, hematocrit, platelets, differential count (neutrophils, eosinophils, basophils, monocytes, lymphocytes).

Clinical Chemistry	

Sodium, potassium, chloride, bicarbonate, non-fasting glucose, urea, creatinine, creatine kinase (CK), protein, albumin, phosphate, calcium, total and direct bilirubin, alkaline phosphatase, ALT, AST, urate, hSCRP, GGT

Coagulation	

Prothrombin time (i.e., INR) and activated thromboplastin time (aPTT).

Viral Serology	

HIV (specific tests HIV-1 antibody, HIV-1/2 antibody, HIV-2 antibody), hepatitis B surface antigen (HBsAg), total hepatitis B core antibody (HBcAb), hepatitis C virus (HCV) by PCR.

Pregnancy Test	

All women of childbearing potential (including those who have had a tubal occlusion/ligation) will have a blood pregnancy test at screening. Urine pregnancy tests will be performed at specified subsequent visits. If a urine pregnancy test is positive, it must be confirmed by a blood pregnancy test.

Urinalysis	

Specific gravity

Dipstick: pH, glucose, protein, blood.

If there is a clinically significant positive result (confirmed by a positive repeated sample), urine will be sent to the laboratory for microscopy and culture. If there is an explanation for the positive dipstick results (e.g., menses), it should be recorded and there is no need to perform microscopy and culture.

Microscopic examination (red blood cells [RBCs], white blood cells [WBCs], casts, crystals, epithelial cells, bacteria), if blood or protein is abnormal.

Other Screening Tests	

Urine drug screen (to include at minimum: amphetamines, barbiturates, cocaine, opiates, and benzodiazepines).

Alcohol breath or blood test (as per local procedure).

Clostridium difficile (ELISA)

Ova and parasite stool examination

Other Tests	

IgE

Tryptase

The results of each test must be entered into the CRF.

Investigators must document their review of each laboratory safety report.

Laboratory results that could unblind the study that are performed centrally will not be reported to investigative sites or other blinded personnel until the study has been unblinded.

## **Additional Statistical Considerations for Clinical Laboratory Data**

- **Standard Reference Ranges and Transformation of Data**

Roche standard reference ranges, rather than the reference ranges of the Investigator, will be used for all parameters. For most parameters, the measured laboratory test result will be assessed directly using the Roche standard reference range. Certain laboratory parameters will be transformed to Roche's standard reference ranges.

A transformation will be performed on certain laboratory tests that lack sufficiently common procedures and have a wide range of Investigator ranges, e.g., enzyme tests that include AST, ALT, and alkaline phosphatase and total bilirubin. Since the standard reference ranges for these parameters have a lower limit of zero, only the upper limits of the ranges will be used in transforming the data.

- **Definition of Laboratory Abnormalities**

For all laboratory parameters included, there exists a Roche predefined standard reference range. Laboratory values falling outside this standard reference range will be labeled "H" for high or "L" for low in participant listings of laboratory data.

In addition to the standard reference range, a marked reference range has been predefined by Roche for each laboratory parameter. The marked reference range is broader than the standard reference range. Values falling outside the marked reference range that also represent a defined change from baseline will be considered marked laboratory abnormalities (i.e., potentially clinically relevant). If a baseline value is not available for a participant, the midpoint of the standard reference range will be used as the participant's baseline value for the purposes of determining marked laboratory abnormalities. Marked laboratory abnormalities will be labeled in the participant listings as "HH" for very high or "LL" for very low.

## **Appendix 5**

### **Contraceptive Guidance and Collection of Pregnancy Information**

#### **1. DEFINITIONS**

- **Woman of Childbearing Potential (WOCBP)**

A woman is considered fertile following menarche and until becoming post-menopausal unless permanently sterile.

- **Women in the following categories are considered to be Woman of Non-Childbearing Potential (WONCBP)**

a. Pre-menarchal

b. Pre-menopausal female with one of the following:

- Documented hysterectomy.

- Documented bilateral salpingectomy.

- Documented bilateral oophorectomy.

Note: Documentation can come from the site personnel's: review of participant's medical records, medical examination, or medical history interview.

c. Post-menopausal female

- A post-menopausal state is defined as no menses for  $\geq$  12 months without an alternative medical cause other than menopause. A high follicle-stimulating hormone (FSH) level in the post-menopausal range may be used to confirm a post-menopausal state in women not using hormonal contraception or hormonal replacement therapy (HRT). However, in the absence of 12 months of amenorrhea, a single FSH measurement is insufficient.

- Females on HRT and whose menopausal status is in doubt will be required to use one of the non-hormonal highly effective contraception methods if they wish to continue their HRT during the study. Otherwise, they must discontinue HRT to allow confirmation of post-menopausal status before study enrollment.

## 2. CONTRACEPTION GUIDANCE

### • **Female Participants**

Female participants of childbearing potential are eligible to participate if they agree to use a highly effective method of contraception consistently and correctly as described in [Table 1](#) below.

Per ICH M3(R2), highly effective methods of birth control are defined as those, alone or in combination, that result in a low failure rate (i.e., less than 1% per year) when used consistently and correctly.

**Table 1 Highly Effective Contraceptive Methods**

Highly Effective Contraceptive Methods That Are User-Dependenta (Failure rate of <1% per year when used consistently and correctly)
Combined (estrogen- and progestogen-containing ) hormonal contraception associated with inhibition of ovulation 

• Oral

• Intravaginal

• Transdermal

Progestogen-only hormonal contraception associated with inhibition of ovulation 

• Oral

• Injectable

Highly Effective Methods That Are User-Independenta

• Implantable progestogen-only hormonal contraception associated with inhibition of ovulation

• Intrauterine device (IUD)

• Intrauterine hormone-releasing system (IUS)

• Bilateral tubal occlusion/ligation

Vasectomized partner A vasectomized partner is a highly effective contraception method provided that the partner is the sole male sexual partner of the WOCBP and the absence of sperm has been confirmed. If not, an additional highly effective method of contraception should be used.
Sexual abstinence Sexual abstinence is considered a highly effective method only if defined as refraining from heterosexual intercourse during the entire period of risk associated with the study treatment. The reliability of sexual abstinence needs to be evaluated in relation to the duration of the study and the preferred and usual lifestyle of the participant.

a) Typical use failure rates may differ from those when used consistently and correctly. Use should be consistent with local regulations regarding the use of contraceptive methods for participants participating in clinical studies.

### **3. PREGNANCY TESTING**

For WOCBP enrolled in the study, blood sample and urine pregnancy tests will be performed according to Schedule of Activity tables (see Section 1.3). If a urine pregnancy test is positive, it must be confirmed by a blood pregnancy test.

Pregnancy testing will be performed whenever a menstrual cycle is missed or when pregnancy is otherwise suspected and according to local practice.

### **4. COLLECTION OF PREGNANCY INFORMATION**

- Male participants with partners who become pregnant**

The Investigator will attempt to collect pregnancy information on any male participant's female partner who becomes pregnant while the male participant is in this study (see Section 8.3.5 Pregnancy). This applies only to male participants who receive RO7049665.

Attempts should be made to collect and report details of the course and outcome of any pregnancy in the partner of a male participant exposed to study treatment. The Investigator will record pregnancy information on the Clinical Trial Pregnancy Reporting Form and submit it to the Sponsor within 24 hours of learning of the partner's pregnancy. When permitted by the site, the pregnant partner would need to sign an Authorization for Use and Disclosure of Pregnancy Health Information to allow for follow-up on her pregnancy. If the authorization has been signed, the Investigator should update the Clinical Trial Pregnancy Reporting Form with additional information on the course and outcome of the pregnancy when available. An Investigator who is contacted by the male participant or his pregnant partner may provide information on the risks of the pregnancy and the possible effects on the fetus, to support an informed decision in cooperation with the treating physician and/or obstetrician. The female partner will be followed to determine the outcome of the pregnancy. Information on the status of the mother and child will be forwarded to the Sponsor. Monitoring of the participant's partner should continue until conclusion of the pregnancy. Any termination of the pregnancy will be reported regardless of fetal status (presence or absence of anomalies) or indication for procedure.

- Female participants who become pregnant**

The Investigator will collect pregnancy information on any female participant, who becomes pregnant while participating in this study (see Section 8.3.5 Pregnancy). Information will be recorded on the appropriate form and submitted to the Sponsor within 24 hours of learning of a participant's pregnancy. The participant will be followed to determine the outcome of the pregnancy. The Investigator will collect follow-up information on the participant and the neonate, which will be forwarded to the Sponsor. Monitoring of the participant should continue until conclusion of the pregnancy. Any

termination of pregnancy will be reported, regardless of fetal status (presence or absence of anomalies) or indication for procedure.

While pregnancy itself is not considered to be an AE or SAE, and should not be recorded on the AE eCRF, any pregnancy complication will be reported as an AE or SAE. A spontaneous abortion is always considered to be an SAE and will be reported as such. Any post-study pregnancy related SAE considered reasonably related to the study treatment by the Investigator, will be reported to the Sponsor as described in [Appendix 2](#). While the Investigator is not obligated to actively seek this information in former study participants, he/she may learn of an SAE through spontaneous reporting.

Any female participant who becomes pregnant while participating in the study will be withdrawn from the study.

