## **6. TREATMENTS**

Study treatment is defined as any investigational treatment(s), marketed product(s), placebo, or medical device(s) intended to be administered to a study participant according to the study protocol.

The investigational medicinal product (IMP) required for completion of this study will be provided by the Sponsor. Study drug will be administered by the investigational staff (i.e., Investigator or study nurse) at the study center under supervision of the Investigator.

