### **6.3.2 Blinding**

This study is double-blinded. For this study it means that the participant, the Investigator(s), and all individuals in direct contact with the participant at the investigative site will be blinded. Members of the Sponsor's project and study teams who do not have direct contact with the participant may be unblinded.

To allow informed recommendations or decisions regarding the dose-selection in this study, an integrated assessment of the safety, tolerability and available PK and/or PD will be made prior to each dose-decision.

If required, unblinded data (individual as well as at group level) may also be presented to the Drug Safety Committee or IMC or other experts of the Sponsor and at group level to the PI.

The IVRS/IWRS will be programmed with blind-breaking instructions. The blind may be broken if, in the opinion of the Investigator, it is in the participant's best interest to know the study treatment assignment. The Sponsor must be notified before the blind is broken unless identification of the study treatment is required for a medical emergency in which the knowledge of the specific blinded study treatment will affect the immediate management of the participant's condition (e.g., antidote available). In this case, the Sponsor must be notified within 24 hours after breaking the blind. The date and reason that the blind was broken must be recorded in the source documentation and case report form (CRF), as applicable.

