### **8.3.5      Pregnancy**

Female participants of childbearing potential will be instructed to immediately inform the Investigator if they become pregnant during the study or within 56 days after the last dose of study treatment.

Male participants will be instructed through the ICF to immediately inform the Investigator if their partner becomes pregnant during the study or within 56 days after the last dose of study drug.

If a pregnancy is reported, the Investigator should inform the Sponsor within 24 hours of learning of the pregnancy and should follow the pregnancy reporting process as detailed in [Appendix 5](#).

Abnormal pregnancy outcomes (e.g., spontaneous abortion, fetal death, stillbirth, congenital anomalies, ectopic pregnancy) are considered SAEs ([Appendix 5](#)).

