## **6 CONGENITAL ANOMALIES/BIRTH DEFECTS**

[figure not shown]
Any congenital anomaly/birth defect in a child born to a female participant or female partner of a male patient exposed to study treatment should be classified as a serious adverse event, recorded on the Adverse Event eCRF, and reported to the Sponsor immediately (i.e., no more than 24 hours after learning of the event; see Section 5 of [Appendix 2](#)).

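### Appendix 5 limits partner-pregnancy collection to men on RO7049665, which a blinded investigator cannot apply and other parts of the protocol contradict

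*Combined protocol and SAP*

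**What the plan says.** Appendix 5, Section 4 opens its part on male participants without any arm limit: "The Investigator will attempt to collect pregnancy information on any male participant's female partner who becomes pregnant while the male participant is in this study". The limit follows at once: "This applies only to male participants who receive RO7049665". The next paragraph is broad again, asking for attempts to collect and report the course and outcome of "any pregnancy in the partner of a male participant exposed to study treatment". Section 6 counts placebo as study treatment: "Study treatment is defined as any investigational treatment(s), marketed product(s), placebo, or medical device(s" and so on.

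Section 8.3.5 has no arm limit. "Male participants will be instructed through the ICF to immediately inform the Investigator if their partner becomes pregnant"; the investigator then informs the Sponsor within 24 hours and follows the reporting process in Appendix 5. Abnormal pregnancy outcomes "are considered SAEs". Appendix 2, Section 5 puts pregnancies on its 24-hour reporting list, citing Section 8.3.5, again for either arm.

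On blinding, Section 6.3.2 says that "the participant, the Investigator(s), and all individuals in direct contact with the participant at the investigative site will be blinded". Sponsor team members without direct participant contact may be unblinded.

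**The concern.** The limit is addressed to the investigator, who does not know the assignment. A site reading it literally has two ways forward: ask for the assignment, or wait for the Sponsor to say whether follow-up is wanted. The first is an unblinding with no clinical reason. The second has a similar problem, because an answer given selectively by arm tells the site which arm the man is in.

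What is exposed is mainly the follow-up to outcome. Section 8.3.5 protects the first 24-hour notice, but the collection of course and outcome is set out in Appendix 5, and that is how a later abnormal outcome becomes known. If follow-up were done for one arm only, an abnormal outcome on active drug would have no placebo counterpart collected in the same way. Section 4.2.2 gives help in judging whether AEs are drug related as a reason for having the placebo arm.

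**Working it through.** This is a question of wording, so the check is to set the relevant texts side by side.

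| Text | Who is covered | Limited to active arm? |
|---|---|---|
| Appendix 5 §4, first sentence | any male participant's partner | No |
| Appendix 5 §4, second sentence | men who receive RO7049665 | **Yes** |
| Appendix 5 §4, next paragraph | partners of men exposed to study treatment | No (Section 6 includes placebo) |
| Appendix 5 §4, female participants | any female participant | No |
| Appendix 5 §5 | any spontaneous abortion is an SAE | No |
| Appendix 5 §6 | a congenital anomaly, including in a child of a "female partner of a male patient exposed to study treatment should be classified as a serious adverse event" | No (Section 6 includes placebo) |
| Section 8.3.5 | all male participants; 24-hour report; abnormal outcomes are SAEs | No |
| Appendix 2 §5 | all pregnancies on the 24-hour list | No |
| Section 5.1, contraception for men | RO7049665 or placebo | No |

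The restricting sentence is the only one with an arm limit.

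**Can the site apply it?** It would need the assignment, which Section 6.3.2 withholds. That section lets the investigator break the blind when this is judged to be in the participant's best interest. Deciding whether to complete a pregnancy form is not such a reason.

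**Does the other text settle the matter?** Only in part. Section 8.3.5 requires the initial report for every man, but refers to Appendix 5 for the process, and the process contains the limit. Appendix 2 points back to Section 8.3.5. The cross-references therefore end at the contradictory paragraph.

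**Size.** Inputs are the 4:1 allocation (Section 6.3.1), up to 65 participants and about 10 per cohort (Section 9.2).

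- Placebo share: 1/(4+1) = 20%.
- Placebo participants: 65 × 1/5 = 13. Active: 65 × 4/5 = 52.
- Per cohort of 10: 10 × 1/5 = 2 on placebo.
- Men on placebo: between 0 and about 13, because the documents do not give the number of men.
- If the sentence were enforced over everything else, and men were spread equally across arms, about 20% of men would fall outside collection, all of them on placebo. This is an upper bound.
- Chance that a man unblinded for this reason is on active drug: 4/5 = 80%.

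**The plan's own figures.** Section 9.2 gives the chance of seeing at least one AE with a true rate of 20%: 83% with 8 participants and 59% with 4. These reproduce: 1 − 0.8^8 = 0.832 and 1 − 0.8^4 = 0.590. They do not enter this point and do not change if the sentence is corrected.

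**The case against.** The strongest reply is that nothing need go wrong. A blinded site that follows Section 8.3.5, Appendix 2 Section 5 and Appendix 5 Sections 5 and 6 collects from every man and never needs the assignment. Nothing in Appendix 5 instructs anyone to unblind. If the Sponsor wanted an arm limit, its unblinded staff could apply it away from the site. Partners are not randomized or dosed and so are not in the Safety population (Table 6). Table 7 lists no partner-pregnancy analysis, and Section 9.1 states no hypotheses. Contraception is required, so few events are expected.

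Most of this stands, and it rules out three stronger readings that a reader might infer.

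- *Partner-pregnancy SAEs go uncollected on placebo.* This would follow only if one sentence overrode all the arm-neutral text.
- *The rule forces unblinding.* The documents do not say so. Section 6.3.2 ties unblinding to the participant's best interest, and filtering by the Sponsor is possible. There is a risk of unblinding, not a requirement.
- *One such unblinding costs a cohort about half of its blinded control.* That could apply only if the man is on placebo, about 1 chance in 5. Even then he stays in the Safety population and his data are kept.

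The reply does not remove the contradiction. Section 8.3.5 relies on Appendix 5 for the process, so a site must choose between conflicting sentences. Filtering by the Sponsor would keep the site blind only if no arm-selective request came back to the site, and it would still make follow-up depend on arm.

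**Conclusion.** The point holds as an internal contradiction: a stated operational rule that cannot be followed under the blind and that conflicts with every neighbouring provision on pregnancy reporting. The consequence is a risk, not a certainty, of unnecessary unblinding or of arm-dependent follow-up to pregnancy outcome.

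It is minor. It touches at most about 13 placebo participants, fewer if some are women, and only those whose partner becomes pregnant. No planned table, estimate or sample-size figure changes. The range assumes the full 65 are enrolled and 4:1 is achieved. It is still worth correcting, because the correction is simple and the present text gives the site no consistent instruction.

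**What to change.** In Appendix 5, Section 4, replace the restricting sentence with: *This applies to all male participants who receive study treatment (RO7049665 or placebo); treatment assignment must not be unblinded to decide whether to collect it.* This brings the paragraph into line with Sections 6, 6.3.2 and 8.3.5, Appendix 2 Section 5 and Appendix 5 Section 6. The unblinding provisions in Section 6.3.2 stay as they are.

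The cost is one sentence in the next amendment, matching guidance for the pregnancy reporting form, and at most a few extra placebo-arm follow-ups.

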## **5 ABORTIONS**

Any spontaneous abortion should be classified as a serious adverse event (as the Sponsor considers spontaneous abortions to be medically significant events), recorded on the Adverse Event eCRF, and reported to the Sponsor immediately (i.e., no more than 24 hours after learning of the event; see Section 5 of [Appendix 2](#)).

Any induced abortion due to maternal toxicity and/or embryo-fetal toxicity should also be classified as serious adverse event, recorded on the Adverse Event eCRF, and reported to the Sponsor immediately (i.e., no more than 24 hours after learning of the event; see Section 5 of [Appendix 2](#)).

Elective abortion not associated with toxicity (e.g., induced abortion for personal reasons) does not require expedited reporting but should be reported as outcome of pregnancy on the Clinical Trial Pregnancy Reporting Form.

## **6 CONGENITAL ANOMALIES/BIRTH DEFECTS**

[figure not shown]
Any congenital anomaly/birth defect in a child born to a female participant or female partner of a male patient exposed to study treatment should be classified as a serious adverse event, recorded on the Adverse Event eCRF, and reported to the Sponsor immediately (i.e., no more than 24 hours after learning of the event; see Section 5 of [Appendix 2](#)).

## Appendix 6 Pain and Skin Reactivity Assessments

## Pain Assessment:

Pain will be assessed by the participant according to a 100-mm horizontal VAS:

- 0 = no pain,
- 100 = worst pain imaginable.

